1 PROTOCOL REVISION HISTORY

24 Feb 2014 By	Final Version
PPD	

5 SYNOPSIS

Compound:	WTX101
Clinical Indication:	Wilson Disease (WD)
Study Phase and Type:	Phase 1 – Drug absorption and food-effect
Study Objectives:	 The primary objectives of the study are to evaluate: The effect of dosing with an Enteric coated (EC) tablet versus dosing with the current non-coated capsule administered with a proton pump inhibitor (PPI; omeprazole) under fasting conditions on the absorption of WTX101. The effect of dosing an EC tablet with and without food on the absorption of WTX101 The safety and tolerability of WTX101.
Summary of Study Design:	This will be a single-center, open-label, randomized, 3-period, 3-treatment, 6-sequence crossover study evaluating the absorption of WTX101 after single doses in healthy subjects based on the measurement of plasma total molybdenum (Mo). This study consists of a screening phase, three periods with similar procedures, and an end-of-study (EOS) visit. Screening of subjects will occur within 28 days prior to the first WTX101 dose.
	Subjects randomized to receive PPI in Period 1 (Treatment C) will report to the Clinical Research Unit (CRU) on Day -5, i.e. 5 days prior to first dosing with WTX101, to receive a morning dose of omeprazole under fasting conditions. These subjects will be given a container with omeprazole doses and will continue once daily (QD) administration of omeprazole under fasting conditions on an outpatient basis, until their return to the CRU for check-in on Day -1. To ensure that the planned number of subjects are dosed with WTX101 on Day 1 of Period 1, stand-by subjects will also receive QD doses of omeprazole, as described above. Should any subject withdraw from the study after omeprazole administration, but before receiving WTX101 in Period 1, they will be replaced with a stand-by subject.
	Subjects randomized to receive PPI in Periods 2 or 3 will receive the container with omeprazole doses prior to discharge from the CRU after the 192-hour post-dose procedures in Period 1 or Period 2, as appropriate. These subjects will initiate

	QD administration of omeprazole under fasting conditions at home the following day and continue until their return to the CRU for their next admission.
	In each of the 3 periods, all subjects (Treatments A, B, and C) will be admitted to the CRU on Day -1, and will receive WTX101 EC tablets alone under fasting conditions (Treatment A); WTX101 EC tablets alone under fed conditions (Treatment B); or, omeprazole under fasting conditions followed by WTX101 non-coated capsules under fasting conditions (Treatment C). Pharmacokinetic (PK) sampling (for the measurement of plasma concentrations of total elemental Molybdenum (Mo)) will be obtained at the following timepoints while subjects remain in the CRU: Time 0 (within 1 hour predose), and then 1, 2, 3, 3.5, 4, 4.5, 5, 6, 7, 7.5, 8, 8.5, 9, 9.5, 10, 12, 14, 16, 24, 36, and 48 hours postdose. Subjects will be discharged on Day 3 following the 48 hours postdose procedures, unless medically necessary to extend confinement to 72 hours.
	Subjects will be required to return to the CRU for outpatient visits on 6 consecutive days (Days 4, 5, 6, 7, 8 and 9) in each period, for subsequent PK sampling and procedures at: 72, 96, 120, 144, 168, and 192 hours postdose.
	The exact time points for collection of PK samples may be amended following evaluation of the data from the ongoing Study WTX101-101. If this is required it will be confirmed prior to study start. However, the total volume of blood taken for PK sample analysis will not be increased from that stated in Section 11.1.5.3
	The washout between WTX101 doses in each period will be at least 14 days.
	Subjects will return to the CRU 14 days (+/-2 days) after the final study medication administration for an EOS visit with follow-up procedures, and to determine if any adverse event (AE) has occurred since the last study visit. Subjects who terminate the study early should be seen and assessed by an Investigator, whenever possible, to undergo the procedures associated with the EOS visit.
	Safety will be monitored throughout the study.
Study Duration:	Subjects who complete the study may be involved in the study for up to 48 days excluding screening (Day -5 of period one to the EOS visit). The study has a screening phase (Day -28 to Day -5 of Period 1); three study periods (Periods 1, 2, and 3 comprised of Day -5 to Day 9); and, an EOS visit 14 days (+/- 2 days) following the final administration of WTX101. Each period will be separated by a washout of at least 14 days

	between administrations of WTX101.	
	The entire study is expected to last 48 days from the first subject dosed to last subject-last visit (LSLV).	
Blinding:	This is an open-label study.	
Number of Subjects:	Eighteen (18) healthy, non-tobacco using adult male and female subjects between 19 and 55 years of age (inclusive).	
Dosage, Dosage Form, Route, and Dose Regimen:	WTX101 will be supplied as non-coated capsules or EC tablets for oral administration. Each WTX101 non-coated capsule (hydroxypropyl methylcellulose [HPMC]) contains 30 mg of bis- choline tetrathiomolybdate and the following excipients: anhydrous di-calcium phosphate and anhydrous sodium carbonate. Each WTX101 EC tablet contains 30 mg of bis- choline tetrathiomolybdate and the following excipients: tri- calcium phosphate, sodium carbonate, sodium starch glycolate, magnesium stearate. WTX101 EC Tablets are coated with Opadry 03K19229 Clear and Acryl-Eze White.	
	Dose regimens are described as follows:	
	Treatment A: 60 mg WTX101 (2 x WTX101 EC tablets, 30mg) at Hour 0 on Day 1 following an overnight fast.	
	Treatment B: 60 mg WTX101 (2 x WTX101 EC tablets, 30mg) at Hour 0 on Day 1, 30 minutes after the start of a high-fat breakfast, preceded by an overnight fast.	
	Treatment C: 20 mg omeprazole (1 x 20 mg delayed-release capsule) QD on the mornings of Days -5 to -1 following an overnight fast, 20 mg omeprazole capsule at Hour -1 on Day 1 following an overnight fast, and 60 mg WTX101 (2 x WTX101 non-coated capsules, 30mg) at Hour 0 on Day 1	
	All study medications (WTX101 non-coated capsules, WTX101 EC tablets and Omeprazole) should be administered orally with approximately 240 mL of room temperature water. The EC Tablets and non-coated capsules must be swallowed whole.	
Stopping Rules	Safety-related individual- and study-specific stopping criteria are detailed below:	
	Dosing will be discontinued for an individual subject experiencing any National Cancer Institute (NCI) Common Terminology Criteria for Adverse Events (CTCAE) version 4.0 (CTCAE v. 4.0) Grade 3 or higher event that is assessed as treatment-related.*	
	The study will be stopped if:	

	 2 or more subjects experience an NCI CTCAE v. 4.0 Grade 3 or higher event that is assessed as treatment-related*, or if 1 or more subjects experience a Grade 4 or higher event that is assessed as treatment-related*. *Treatment-related is defined as likely, probably, or possibly related per Section 11.1.6.3 of the protocol. 	
Key Assessments:	Pharmacokinetics:The plasma concentrations of WTX101 will be measured by plasma concentrations of total elemental Mo.The following PK parameters will be calculated for total Mo in plasma: AUC _{0-t} , AUC _{0-inf} , C _{max} , t _{max} , λz , t _{1/2} , CL/F, and Vz/F. Descriptive statistics will be computed for all parameters. The parameters C _{max} , AUC _{0-t} , and AUC _{0-inf} will be compared among treatments using an analysis of variance (ANOVA) on the In- transformed values. T _{max} will be compared among treatments using non-parametric statistic, i.e. Wilcoxon Rank Sum.	
	Safety: Safety will be monitored through physical examinations, vital sign measurements, electrocardiograms (ECGs), AEs and clinical laboratory tests. Summary statistics for the laboratory safety tests, ECGs, and/or vital signs will be computed and provided.	

WTX101 EC Drug Absorption and Food Effect Study Protocol Wilson Therapeutics

Sponsor Project No.: WTX101-102 Celerion Project No.: CA13895 US IND No.: 119,006

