8.2 Rationale

8.2.1 Rationale for this Study and Study Design

This study is designed to meet the objectives outlined in Section 9.

WTX101 is an oral de-coppering agent. It is a bis-choline salt of tetrathiomolybdate, bis[(2-hydroxyethyl)trimethylammonium] tetrathiomolybdate.

In previous studies, coadministration of PPIs has been shown to increase the bioavailability of tetrathiomolybdate (as a consequence of increased gastric pH) and to reduce gastrointestinal side effects.⁴ An Enteric Coated (EC) tablet formulation would be expected to offer the same benefits of increased bioavailability and reduced gastrointestinal side effects while avoiding the need to coadminister a PPI.

This study will be conducted as a crossover study, aimed at evaluating the absorption of WTX101 from the EC tablet under fed and fasted conditions and compared to the current non-coated capsule administered with a proton pump inhibitor (under fasting conditions) in order to Confirm the in vivo performance characteristics, including the absorption profile, and food effect of the EC tablet in man.

Subjects will be randomized to one of six treatment sequences to minimize assignment bias. A crossover design is used to control the variability between subjects. The washout period between WTX101 doses is considered sufficient to prevent carryover effects of the treatments.

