8.2.3 Rationale for Endpoints

The primary endpoints will be the AUCs and C_{max} , as these PK parameters are the most relevant to characterize the rate and extent of exposure following WTX101 administration - from the treatments to be tested.

Other parameters will also be presented, including: t_{max} , λz , and $t_{\frac{1}{2}}$, CL/F, and Vz/F.

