9.2 Study Endpoints

The primary endpoints are:

- Plasma concentrations and PK parameters (e.g., AUC_{0-inf}, AUC_{0-t}, C_{max}, t_{max}, λz, and t_½, CL/F, and Vz/F) for total Molybdenum (Mo) following WTX101 EC tablet administration under fasting and fed conditions and WTX101 non coated capsule coadministered with a PPI under fasting conditions
- Safety and tolerability will be evaluated based on physical examinations, vital sign measurements, Electrocardiogram (ECGs), AEs, and clinical laboratory tests.

[figure not shown]

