10.5.2 Method of Randomizing Subjects to Treatment Groups

Each subject will be assigned a unique identification number upon screening. Subjects who complete the study screening assessments and meet all the eligibility criteria will receive the corresponding product, according to a randomization scheme generated at Celerion. To ensure that the planned number of subjects are dosed with WTX101 on Day 1 of Period 1, additional, stand-by subjects (who also complete the study screening assessments and meet all eligibility criteria) will also receive QD doses of omeprazole. Subjects will be considered randomized when they receive the first dose of WTX101 on Day 1 of Period 1.

Subjects will receive each treatment on one occasion. The sequences to be used in the randomization will be ABC, ACB, BAC, BCA, CAB, and CBA.

Subjects may be replaced at the discretion of the Sponsor.

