12.2 Statistical Methods

Detailed methodology for summary and statistical analyses of the data collected in this trial will be documented in a Statistical Analysis Plan (SAP). The SAP will be prepared by

Celerion and agreed upon with the Sponsor. This SAP will not include any pharmacokinetic analysis. Additionally, a separate Pharmacokinetic Analysis Plan (PKAP) will be prepared by Kramer Consulting LLC and agreed upon with the Sponsor. This document may modify the plans outlined in the protocol; however, any major modifications of the primary endpoints definition and/or its analysis will also be reflected in a protocol amendment. Additional statistical analyses other than those described in this section may be performed if deemed appropriate and included in the SAP/PKAP.

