12.2.2 Descriptive Statistics

Arithmetic means, standard deviations (SD), sample size, coefficient of variation (CV), median, minimum and maximum values will be calculated for the plasma concentrations and the PK parameters listed in Section 12.1. Geometric means will be calculated only for AUC and C_{max} parameters.

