12.2.3 Analysis of Variance

An analysis of variance (ANOVA) will be performed on the In-transformed AUC_{0-t} , AUC_{0-inf} and C_{max} . The ANOVA model will include sequence, treatment, and period as fixed effects, and subject nested within sequence as a random effect. Sequence will be tested using subject nested within sequence as the error term at a 10% level of significance. Each ANOVA will include calculation of geometric least-squares means (GLSM), the difference between treatment GLSM, and the standard error associated with this difference. The above statistical analyses will be done using SAS[®] PROC GLM.

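### The synopsis fixes the Wilcoxon rank-sum test, a test for independent samples, for t_max in a crossover where every comparison is within subject

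*Protocol*

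**What the plan says.** The Key Assessments row of the synopsis (Section 5) states that t_max "will be compared among treatments using non-parametric statistic, i.e. Wilcoxon Rank Sum". This is the only place in the protocol that names a test for t_max.

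The design is a three-period, three-treatment, six-sequence crossover in 18 subjects. Section 10.5.2 says "Subjects will receive each treatment on one occasion", and Section 8.2.1 gives the reason for the design: "A crossover design is used to control the variability between subjects".

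For ln-transformed AUC and C_max, Section 12.2.3 respects that structure: "The ANOVA model will include sequence, treatment, and period as fixed effects, and subject nested within sequence as a random effect". Section 12.2.4 lists two comparisons, B with A and A with C.

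The standing of t_max is not consistent. Section 8.2.3 takes the AUCs and C_max as primary and places t_max after "Other parameters will also be presented, including". Section 9.2 includes it in the list that opens "The primary endpoints are".

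**The concern.** Each t_max comparison sets two values from the same subject against each other. The rank-sum test treats them as coming from different people. It therefore leaves between-subject variation in the yardstick, which is the variation the crossover was chosen to remove. It also makes no allowance for period.

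With positive within-subject correlation, the test's variance for the treatment difference is too large and its p-values are too large. A modest delay or advance in absorption (fed against fasted, coated tablet against capsule with omeprazole) could then be reported as not significant when a paired test would have shown it. The study objectives concern absorption, and t_max is the parameter that speaks most directly to its timing.

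**Working it through.** **Reading the text.** The synopsis fixes the test by name and applies it to t_max across treatments. It does not mention within-subject or period differences. A rank-sum test on period differences between sequence groups can be valid in a two-period crossover, but neither the wording nor the three-period design points to that.

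**Inputs from the protocol.** There are 18 subjects (Section 5), each treated once with A, B and C (10.5.2). There are 27 post-dose sampling times from 1 to 192 h (10.1). Section 12.2.1 says the sample size had no statistical basis, so there is no power figure to reproduce.

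**Assumed inputs, because the protocol gives none.** Two-sided 5% level; lognormal t_max with median 4.5 h and total log-SD 0.35; within-subject correlation ρ from 0 to 0.7; shifts of 20% to 75%.

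**Step 1: direction, by normal approximation.** With n subjects and common variance σ², an independent-samples test uses variance 2σ²/n for the difference. The true variance in paired data is 2σ²(1 − ρ)/n. The actual size of a nominal 5% test is therefore

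2 × [1 − Φ(1.96 / √(1 − ρ))]

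- ρ = 0: 1.96/1.000 = 1.96, size 5.0%
- ρ = 0.3: 1.96/0.837 = 2.34, size 1.9%
- ρ = 0.5: 1.96/0.707 = 2.77, size 0.6%
- ρ = 0.7: 1.96/0.548 = 3.58, size 0.03%
- ρ = −0.3: 1.96/1.140 = 1.72, size 8.6%

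**Step 2: size and power by simulation.** Correlated lognormal t_max for two treatments in 18 subjects was rounded to the nearest sampling time. The rank-sum and signed-rank tests were then applied, with 4000 replicates per cell (Monte Carlo standard error at most 0.8 points). Entries are rank-sum / signed-rank, in %.

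| | ρ = 0 | ρ = 0.3 | ρ = 0.5 | ρ = 0.7 |
|---|---|---|---|---|
| Type I error | 4.6 / 5.1 | 2.3 / 4.9 | 1.2 / 5.2 | 0.2 / 4.7 |
| Power, 20% shift | 31 / 29 | 29 / 40 | 27 / 51 | 22 / 71 |
| Power, 35% shift | 66 / 64 | 70 / 79 | 73 / 89 | 76 / 99 |
| Power, 50% shift | 91 / 89 | 93 / 96 | 96 / 99 | 98 / 100 |

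At a 75% shift both tests reach at least 99%.

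**Step 3: stability.** Separate repeat simulations, one of them with median 5 h, put the rank-sum type I error at 1.6% to 2.4% for ρ = 0.3 and 0.6% to 1.2% for ρ = 0.5. Repeats at median 4.5 h reproduced the power figures within about 2 points.

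**Step 4: sensitivity at ρ = 0.5** (2000 replicates, standard error at most 1.1 points).

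| Log-SD | 20% shift | 50% shift |
|---|---|---|
| 0.25 | 54 / 78 | 100 / 100 |
| 0.35 | 27 / 51 | 96 / 99 |
| 0.50 | 9 / 28 | 67 / 86 |

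Moving the median to 3 h or 8 h changes these by about 2 points or less.

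**The case against.** The strongest case is that little hangs on this p-value.

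- **Weight.** Section 8.2.3 makes the AUCs and C_max primary. Section 9.2 names t_max only as an example, alongside parameters that receive no comparative test. No level, margin or decision rule is attached to t_max. It is still described, since Section 12.2.2 says "median, minimum and maximum values will be calculated for the plasma concentrations and the PK parameters listed in Section 12.1". All of this stands, and it limits the importance of the point. It does not make the named test suitable.
- **Deferral.** Section 12.2 leaves pharmacokinetic methods to a separate analysis plan and adds "This document may modify the plans outlined in the protocol". That plan may already name a paired test. But the protocol did not leave the test open; it fixed one that does not fit the design.
- **Charitable reading.** The clause may be a slip for signed-rank, or shorthand for ranks of period differences. Either is possible, and either would need to be written down.
- **Assumed inputs.** The loss depends on ρ. For a 20% shift, power is 31% against 33% at ρ = 0.1 and 28% against 34% at ρ = 0.2; the large gaps need ρ of 0.5 or more. This stands. The error is also conservative only for positive ρ: at ρ = −0.3, simulation gives a type I error of about 7.4% to 7.8%. That is a further way in which the test misses its nominal level.
- **Period.** A plain signed-rank test has no period term either. This is fair and bears on the choice of remedy, but the signed-rank test does correct the main fault, the ignored pairing.

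**Conclusion.** The concern holds. The synopsis names a test for independent samples where the design makes every comparison within subject, and nothing else in the protocol corrects it.

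The direction follows from the pairing alone: positive correlation makes the test conservative and negative correlation makes it liberal. The amount rests on the assumed level, median, spread, correlation and shift. On those assumptions the cost is nil at ρ = 0, 11 points of power at ρ = 0.3 (40 − 29) and 24 points at ρ = 0.5 (51 − 27) for a 20% shift. For a 50% shift it is at most 3 points at log-SD 0.35, but 19 points (86 − 67) at log-SD 0.50 and ρ = 0.5.

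Only the t_max comparison is affected. The point should be fixed, but it does not threaten the study's main conclusions.

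**What to change.** Replace the synopsis clause with wording such as: *t_max will be compared for B vs A and A vs C using the Wilcoxon signed-rank test on within-subject differences.* Put the same sentence in Section 12.2, so that the body of the protocol also states the method.

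A period-adjusted alternative is equally acceptable, for example rank tests on within-subject period differences stratified by sequence pair. It would match the period term in the ANOVA. If the plain signed-rank test is chosen, equal allocation to the six sequences (18/6 = 3 subjects each) balances period between the two treatments in each comparison, although a period effect would still add spread to the differences. A Hodges-Lehmann median difference with a 90% confidence interval is an optional addition.

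The cost is one sentence in each of two places, carried into the pharmacokinetic analysis plan. No extra data or visits are needed.

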6 STUDY EVENTS FLOW CHART

Study Procedures ^a	S ^b	•			C	-I ^C	Study Days in Each Period ^d																											
Days ightarrow Days	-28	-5	-4	-3	-3 -2 -1 1 2 3 4 5 6 7 8 9								EOS or ET ^e																					
Hours \rightarrow						AM	PM	Pre dose	0^{f}	1	2	3	3. 5	4 4.5	56	67	7.5	8	8.5	99.	5 10	12	14	16 ^g	24	36	48	72	96	120	144	168	192	ET
Administrative Procedures																																		
Informed Consent	Х																																	
Inclusion/Exclusion Criteria	Х						х																											
Medical History	Х																																	
Randomization ^h									х																					ļ				
Safety Evaluations / Others																																		
Physical Examination	х						х																							ļ				х
Height	Х																																	·
Weight	Х						х																											Х
12-Lead ECG	Х						х	х		Х)	ĸ				х				Х			х									Х
Vital Signs (HR, BP, RR & T)	Х						х	х		х)	ĸ				х				х			х									Х
Hem, Chem, UA, and Coag ^j	x						x																			х								х
Serum Cp and Cu	Х																																	
Serum Preg (females only)	Х						х																											Х
FSH (postmen females only)	Х																																	
Urine Alcohol and Drug Screen	Х						х																						$ \rightarrow $			-		
HIV/Hepatitis Screen	Х																															-		
AE Monitoring			-																X														>	
ConMeds		<																>	(>	
Study Medication Administration / PK samples																																		
PPI Administration ^k		х	х	х	х	х		х																										
WTX101 Administration									х																									
Blood for Plasma Total Mo																																		
(PK) ^l								х		х	X	×	x)	K X	x >	×X	Х	х	х	x x	X	X	X	х	X	X	х	х	х	х	х	х	х	
Other Procedures																																		
High-Fat Breakfast ^m								х																										
Confinement in the CRU								<									X									>	>							· · · · · · · · · · · · · · · · · · ·
Return Visits		Х																										Х	х	х	х	х	х	Х

WTX101 EC Drug Absorption and Food Effect Study Protocol Wilson Therapeutics

a. For details on study procedures, refer to Section 11.

- b. Within 28 days of WTX101 first administration.
- C. Subjects will be admitted to the CRU at least 10 hours prior to WTX101 dosing.
- d. Each period will be separated by a washout of at least 14 days between WTX101 doses.
- e. Subjects will be required to return to the CRU approximately 14 days (±2 days) following the final dose of study medication for an EOS evaluation. In the event of early termination, the procedures listed at the end of the study will be performed prior to subject discharge.
- f. Hour 0 corresponds to the time of WTX101 administration. Unless stated otherwise, times listed are in relation to WTX101 dosing.
- g. The 16-hour time point following WTX101 dosing on Day 1 will be either on Day 1 or Day 2, depending on the time of dosing on Day 1.
- h. Please refer to Section10.5.2 for randomization details.
- i. A full physical examination will be performed at screening, check-in, and at the end of the study or upon early termination. A symptom-driven physical examination may be performed at other times, at the Principal Investigator's (PI) discretion.
- j. Samples for serum chemistry will be obtained following a fast of at least 8 hours at screening, and of at least 6 hours at check-in. In case of dropouts, rechecks and postdose serum chemistry, subjects may not have fasted for 6 or 8 hours before the serum chemistry sample is taken.
- k. Subjects randomized to receive Treatment C in Period 1 will be required to come to the CRU in the morning of Day -5 of Period 1 to receive their first dose of PPI (omeprazole). They will receive a properly labeled container which will contain omeprazole doses to be self-administered at home on Days -4 to -1. At the end of Periods 1 and 2, subjects will receive a container with omeprazole doses for self-administration of doses on Days -5 to -1, if they are randomized to receive Treatment C in the next period. Each omeprazole dose self-administered should be taken under fasting conditions, at a time corresponding to Hour -1 relative to the time of dosing WTX101 on Day 1 (Hour 0). Subjects will be given paper diaries to record their self-administered omeprazole doses and whether the dose was administered with food and must return the container (empty or not) and diary at the next visit. The data from the diary will then be transcribed into the eCRF. Home dosing will be monitored daily via attempted contacts (phone calls, texts or emails) whereupon subjects will be reminded to take their medication and queried about AE occurrence.
- I. The exact time points for collection of PK samples may be amended following evaluation of the data from the ongoing Study WTX101-101. If this is required it will be confirmed prior to study start. However, the total volume of blood taken for PK sample analysis will not be increased from that stated in Section 11.1.5.3
- m. Subjects randomized to receive Treatment B will receive breakfast, to be initiated at Hour -0.5 and consumed entirely within the 30 minutes prior to dosing.

Abbreviations: AE = Adverse Event, BP = Blood Pressure, Chem = Serum Chemistry, C-I = Check-in, Coag = Coagulation, ConMeds = Concomitant Medication Monitoring, Cp = Cerulplasmin, CRU = Clinical Research Unit, Cu = Copper, ECG = Electrocardiogram, EOS/ET = End of Study or Early Termination, FSH = Follicle Stimulating Hormone, Hem = Hematology, HIV = Human immunodeficiency virus, HR = Heart Rate, Mo = Molybdenum, PI = Principal Investigator, PK = Pharmacokinetics, Postmen = Postmenopausal, PPI = Proton Pump Inhibitor, RR = Respiration Rate, S = Screening, Serum Preg = Serum Pregnancy Test, T = Temperature, UA = Urinalysis.

